6.7.5 Exploratory Analyses

6.7.5.1 Health Status Outcome

The health status of patients will be assessed using the EQ-5D questionnaire. The EQ-5D measures 5 dimensions of health status: mobility, self-care, usual activities, pain/discomfort, and anxiety/depression. For each dimension, there are 5 levels of response:

- No problems
- Slight problems
- Moderate problems
- Severe problems
- Unable to do / Extreme problems

The number and percent of patients with each response will be presented by dimension at Screening visit and Visit Week 52. The visual analogue scale (VAS) records the patient's parent/caregiver-rated health on a 0 (worst health) to 100 (best health) scale. The VAS score, as well as the change from baseline (Screening visit to Visit Week 52) will be summarized.

A van Elteren (vE) test ([van Elteren 1960](#)) will be used to compare treatment groups on the change from baseline to Visit Week 52 in VAS score.

The Wilcoxon–Mann–Whitney (WMW) test ([Mann and Whitney 1947](#); [Wilcoxon 1945](#)) is widely used nonparametric approach to compare two treatments. In the presence of stratum factors such as baseline age group or baseline cognitive impairment status, the van Elteren (vE) test ([van Elteren 1960](#)), a stratified WMW test, can be used to adjust for the stratification factors.

The treatment effect on change from baseline to Visit Week 52 in VAS score will be tested by the van Elteren test, which is a direct extension of the 2-sample WMW test, and a particular form of the Cochran-Mantel-Haenszel (CMH) test. Baseline age group (either <6 years or ≥ 6 years) and baseline GCA score (either ≤ 70 or >70) will be used as stratification factors in the van Elteren test. It is shown by Qu et al. ([2008](#)) that vE test preserves the type I error rate regardless

of the existence of the stratum effects, and is better than the WMW test when the stratum effects are large.

The null hypothesis being tested is:

H_0 : Two treatment groups produce the same distribution of outcomes

Using one-sided test at the 0.025 level, rejection of H_0 would indicate that the IT treatment group produces more desirable outcomes than no IT treatment group.

The sample SAS code is presented in [appendix 9.2.3](#).

Pharmacoeconomic analyses may be performed by the sponsor staff in the Outcomes Research and Epidemiology group and reported separately in a pharmacoeconomic report to be appended to the Clinical Study Report. Accordingly, any planned pharmacoeconomic analyses related to this data may be described elsewhere.

6.7.5.2 Correlation between Different Neurodevelopmental Assessment Domains

The following correlation coefficients for observed values and change from baseline will be estimated from a linear mixed effects model that takes into account the repeated measures on each patient using the method described by Hamlett et al. (2003) SAS Proc Mixed with restricted maximum likelihood estimation (REML) and an unstructured between and within-patient covariance structure for the random effects will be used for this model.

- GCA standard score from DAS-II and
 - Verbal standard score from DAS-II
 - Nonverbal standard score from DAS-II
 - Spatial standard score from DAS-II
 - SNC standard score from DAS-II
 - ABC standard score from VABS-II
 - Communication standard score from VABS-II
 - Daily Living Skills standard score from VABS-II
 - Socialization standard score from VABS-II
 - Motor Skills standard score from VABS-II
 - CSF GAG levels (log-scale)

- ABC standard score from VABS-II and
 - Communication standard score from VABS-II
 - Daily Living Skills standard score from VABS-II
 - Socialization standard score from VABS-II
 - Motor Skills standard score from VABS-II
 - CSF GAG levels (log-scale)

The sample SAS code is presented in [appendix 9.2.4](#).

Each pair of parameters will also be graphed as scatter plots.

6.7.5.3 Pharmacodynamic Outcome

- CSF and Urine GAG

CSF and Urine GAG observed levels, the change from baseline (Screening Visit) and percent change from baseline will be summarized by visit and treatment group. Mean observed values (\pm SE) and mean percent change compared to baseline will be plotted over time. The percent change compared to baseline is defined as the value at the corresponding visit multiplied by 100 and divided by the baseline value. One decimal will be kept for the percent compared to baseline. A van Elteren (vE) test, described in Section [6.7.5.1](#), will be used to compare treatment groups on the change from baseline and percent change to the Visit Week 52. Baseline age group (either <6 years or ≥ 6 years) and baseline GCA score (either ≤ 70 or >70) will be used as stratification factors in the van Elteren test. Analysis of both CSF total GAG and CSF heparan sulfate if available will be performed.

- CSF Albumin Concentration and Albumin Quotients

Albumin levels will be measured in samples of CSF and serum at Screening, Weeks 4, 16, 28, 40 and Visit Week 52. CSF albumin concentrations, CSF/serum albumin quotients ($Q_{\text{Alb}} = \text{CSF albumin/serum albumin}$) observed levels, the change and the percent change from baseline (Screening Visit) will be summarized by visit and treatment group to assess the blood-CSF barrier function ([Andersson et al. 1994](#)).

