2.5 Pharmacokinetic and Pharmacodynamic Objectives

The PK and PD objectives of this study are:

- To evaluate the concentration of idursulfase and determine PK parameters in serum after IT administration
- To evaluate the concentration of idursulfase in CSF prior to each monthly administration of idursulfase-IT
- To determine the effect of the treatment regimen on the concentration of GAG in CSF

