6.7.4 Subgroup Analyses

Subgroup analyses will be performed for the following subgroups:

- Baseline GCA classification groups. For this analysis, patients with a baseline GCA score of > 70 will be classified as having “Moderate” cognitive impairment, while patients with a baseline GCA score ≤ 70 will be classified as having “Severe” cognitive impairment. The randomization is stratified by this classification variable to ensure treatment group balance within these subgroups
- Baseline age group (either < 6 years or ≥ 6 years)
- Exploratory analysis for baseline age group (either < 55 months or ≥ 55 months).

Subgroup analyses are planned for the change from baseline in GCA and ABC standard scores, respectively. An MMRM model will be used to test for treatment by subgroup interactions. Interactions with a significance level of less than 10% will be considered potentially important and flagged for further clinical assessment. In general, the model will include fixed categorical effects for treatment, visit week, treatment by visit week interaction, subgroup, treatment by subgroup interaction, subgroup by visit interaction and the 3-way interaction between treatment, visit week and subgroup, and genotype. The p-values of interaction terms will be presented, as well as the least squares means and its 95% confidence intervals by treatment and visit for each subgroup classification factor. Descriptive statistics of the observed and change from baseline GCA and ABC standard scores will also be presented by treatment and visit week within each subgroup.

Additionally, the subgroup analysis will be performed for the age subgroup with baseline age < 6 years which may be the patient population with the most potential to benefit from the idursulfase-IT treatment. The change from baseline GCA score obtained at Visit Week 52 will be compared between the treatment groups using MMRM analysis. The repeated measures are the change from baseline GCA score obtained at the scheduled Visit Weeks 16, 28, 40, and 52, respectively. The model will include fixed categorical effects for treatment, visit week, treatment by visit week interaction, baseline GCA classification factor (either ≤ 70 or > 70), treatment by baseline GCA classification factor interaction, genotype and the baseline GCA score as a continuous covariate. Due to small sample size of ITT subjects with baseline age ≥ 6 years, MMRM model will not be applied for this age subgroup.

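### The between-arm comparisons of CSF GAG and EQ-5D VAS have no baseline-adjusted estimate and no confidence interval; adding one is a low-severity improvement

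*SAP*

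**What the plan says.** Protocol 2.5 states the pharmacodynamic objective: "To determine the effect of the treatment regimen on the concentration of GAG in CSF". Protocol 10.6.2 planned a Wilcoxon rank-sum test on change and percent change in CSF GAG. SAP 6.7.5.3 replaces it with a van Elteren test that "will be used to compare treatment groups on the change from baseline and percent change to the Visit Week 52". Baseline age group and baseline GCA class "will be used as stratification factors in the van Elteren test"; the baseline GAG value has no role. The SAP sub-heading covers CSF and urine, so a urine test is implied. The protocol tests CSF only.

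For EQ-5D VAS, SAP 6.7.5.1 says that a van Elteren test "will be used to compare treatment groups on the change from baseline to Visit Week 52 in VAS score", with the same two strata and a one-sided 0.025 level. Percent change is not tested for VAS.

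Descriptive output is planned. For GAG, the observed level, change and "percent change from baseline will be summarized by visit and treatment group", with mean plots over time. VAS score and change are summarised too.

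Nothing elsewhere supplies an estimate. SAP 6.1 offers model-based differences and 95% CIs where relevant for efficacy endpoints. SAP 8.1 requires the baseline score as a covariate in MMRM analyses only. The sample code for the VAS test (SAP 9.2.3) requests no location-shift estimate.

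**The concern.** An objective to determine an effect on a concentration calls for an estimate of that effect against control, with its uncertainty. As planned, the reader gets each arm's summary and a rank-test p-value, and has to work out the contrast and its precision unaided. Change and percent change also give two p-values for one question, and the SAP does not say which leads.

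The second issue is precision. A change score subtracts the whole baseline value whatever its correlation with the Week 52 value, so it over-corrects when that correlation is modest. With about 16 controls, a chance imbalance at baseline passes into the change scores. Both measures are scheduled at Screening and at end of study in both arms, so the adjustment needs no new data.

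**Working it through.** **Inputs.** From SAP 4.2: 48 randomised 2:1 (about 32 v 16), up to 10% missing at Week 52. Evaluable: 32 × 0.9 = 28.8 and 16 × 0.9 = 14.4, so about 29 v 14. The documents give no effect size, SD or power for GAG or VAS, and no baseline to Week 52 correlation r. Those below are assumptions, shown over a range.

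**The plan's own figure.** The only stated power is for GCA: 80% for 11 points with SD 11.6. A noncentral t calculation gives 80.7% (28 v 14) to 81.2% (29 v 14), so it reproduces. It says nothing about GAG or VAS, but it supports the evaluable numbers used here.

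**Variance.** Let the SD be σ at both times.
- Change score: Var = 2σ²(1 − r).
- Baseline-adjusted: Var = σ²(1 − r²).
- Ratio: (1 − r²) / [2(1 − r)] = (1 + r)/2.

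**Power.** The last two columns come from a simulation with 29 v 14 evaluable and an assumed shift of 0.8 SD.

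| r | Variance ratio (1+r)/2 | SE reduction, 1 − √ratio | van Elteren on change | ANCOVA |
|---|---|---|---|---|
| 0.2 | 0.60 | 22.5% | 43% | 65% |
| 0.5 | 0.75 | 13.4% | 63% | 78% |
| 0.7 | 0.85 | 7.8% | 84% | 91% |

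Type I error was 4–5%. At r = 0.9 the SE reduction falls to 2.5%.

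**A skewed marker.** A second simulation used lognormal values (log-scale SD 0.5, four strata with assumed shares 0.4/0.4/0.1/0.1, effect 0.5 log-SD, 3000 trials per setting). Power for van Elteren on change, van Elteren on percent of baseline and ANCOVA on logs was 25%, 27% and 37% at r = 0.5, and 76%, 85% and 89% at r = 0.9. Type I error was 4.4–5.6% for all three.

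**The percent-change definition.** The SAP's percent change compared to baseline "is defined as the value at the corresponding visit multiplied by 100 and divided by the baseline value", which is percent of baseline. It differs from true percent change by a constant 100, so the ranks and the test are the same.

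**CSF GAG under the expected pattern.** Protocol 1.3 reports a pronounced fall at 10 and 30 mg, and Protocol 4.2.1 no appreciable change in untreated patients. With assumed falls of 50–63%, baseline log-SD 0.4–0.5 and treated levels (nearly) independent of baseline, a rank-sum test on percent of baseline (a proxy for van Elteren) and ANCOVA both had about 100% power. At a 33% fall they had 93% and 98%.

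**Coverage of the proposed interval.** If treated patients cluster near a low level while controls track their baseline, slope and residual variance differ by arm, and the smaller arm is the more variable. A common-slope log ANCOVA with ordinary standard errors then under-covers: its nominal 95% interval covered 91–94% in one set of runs and 89–92% in another. HC3 standard errors brought coverage to about 96%.

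**The case against.** The strongest reply is that nothing depends on these tests. They sit under exploratory analyses, outside the three gatekeeping families. SAP 8.5 calls such endpoints supportive and reads their p-values descriptively. The type I error is right. This stands, and it sets the severity.

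It can also be said that the protocol's endpoint is change from baseline in CSF GAG, so a model of log Week 52 values swaps one preference for another. This holds in part: the log scale is a different scale. But once baseline is a covariate, the treatment estimate is the same whether the response is the Week 52 value or the change on that scale. The SAP already uses log-scale CSF GAG in 6.7.5.2, and a rank test on the protocol's quantity is kept.

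The precision gain rests on an unknown r. That stands too: at high r the gain is small, and a rank-based ANCOVA gained nothing at r = 0.7 or above. For CSF GAG, power is hardly in question.

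Three stronger readings are tempting and should not be drawn:
- That the plan reports p-values alone. It does not: means, SDs, medians and plots by arm are planned. The between-arm estimate and its CI are what is missing.
- That VAS is tested on percent change. It is tested on change only.
- That the age strata undermine the test because a stratum holding one arm contributes nothing. SAP 6.7.4 says of patients aged 6 or over that the "MMRM model will not be applied for this age subgroup", but that concerns fitting a model, and the documents do not give the number in that group. Any figure for patients lost this way would rest on a guess.

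**Conclusion.** The gap is real and of low severity. The planned tests are valid, and no confirmatory claim rests on them. For CSF GAG the loss is the estimated effect against control with its interval, which the stated objective calls for; power is not the issue if the expected fall occurs. For VAS, where the documents give no reason to expect a large effect, the loss is the estimate and some precision: a variance ratio of 0.60 to 0.85 for r from 0.2 to 0.7, assuming equal variances at the two times. Little is lost if r is high. The power figures depend further on the assumed shifts and distributions and show direction, not a forecast.

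**What to change.** - **SAP 6.7.5.3:** add an ANCOVA of log(Week 52 CSF GAG) on treatment, GCA class and log(baseline CSF GAG). Report the ratio of geometric means, IT v control, with a 95% CI from HC3 standard errors, because slope and residual variance may differ by arm. Keep one van Elteren test as the distribution-free check, choose change or percent change for it in advance, and state which result leads.
- **SAP 6.7.5.1:** add an ANCOVA of Week 52 VAS on treatment, GCA class and baseline VAS. Report the difference with a 95% CI beside the planned rank test.

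The cost is SAP wording and a few lines of code; SAP 9.2.7 already contains an ANCOVA with an estimate and CI that can be adapted. No new data are needed. The drawbacks are little gain if r is high, and a model assumption, which the robust standard errors and the retained rank test address.

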6.7.5.4 Rate of Change in GCA Score Analysis

The endpoint of rate of change analysis is the slope estimate from the linear regression of GCA score over time for each subject. Only subjects with at least 3 available GCA scores will be included in this analysis.

The slope estimate will be compared between the two treatment groups in HIT-HGT-094 using one-way ANOVA. The response variable in the ANOVA model is the weighted linear regression slope, where the weight is the inverse of one plus the sum of mean squared error (MSE) from the linear regression, i.e. $1/(1+\text{MSE})$.

The sample SAS code is presented in [appendix 9.2.5](#).

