10.5.4 Exploratory Analyses

As exploratory analyses, the primary and key secondary MMRM models will be refit including the continuous baseline covariate by treatment interaction term in the model. Estimated least square means and 95% CIs for each treatment adjusting at the 25th, 50th, and 75th percentiles of the pooled baseline covariate distribution will be evaluated.

Additional subgroup analyses are planned for exploratory purposes for the change from baseline in GCA and ABC scores. An MMRM model will be used to test for subgroup interactions at the 10% significance level. In general, the model will include effects for treatment, visit week, treatment by visit week interaction, subgroup, treatment by subgroup interaction, subgroup by visit interaction and the 3-way interaction between treatment, visit and subgroup. The p-values from interaction tests will be presented, as well as the least square means and 95% CIs by treatment and visit within each subgroup. Descriptive statistics of observed values and change from baseline will also be presented by treatment and visit week within each subgroup.

A subgroup analysis will be performed for baseline GCA groups. For this analysis, patients with a baseline GCA score of greater than 70 will be classified as having “Moderate” cognitive impairment, while patients with a baseline GCA score equal to or below 70 will be classified as having “Severe” cognitive impairment. The randomization is stratified by this classification variable to ensure treatment group balance within these subgroups. Similar exploratory subgroup analyses may be performed for age group (either ≤ 6 years or > 6 years), language, geographic region or other baseline factors using MMRM.

A linear random coefficients model (ie, random slope and intercept for continuous time) will be fit for the primary and key secondary endpoints if appropriate. The average of the subject-specific slope estimates from the model will be compared between treatment groups using the two-sample t-test. To explore the relationship between composite scores and their components, correlations between the GCA and ABC scores (absolute value and change from baseline) and their respective domain scores will be estimated. Scatter plots will also be presented.

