Blinding	
allocation ratio to study arms (32 IT treated and 16 No IT treatment patients). The randomization is stratified by baseline GCA score (≤ 70 and > 70).
 
HGT-HIT-094 is an open label study. Single and double blinding of patients, their families, and the Principal Investigator is not possible due to the absence of a sham device, sham injections, or placebo. The assessors responsible for the DAS-II and VABS-II evaluations will not be informed of patients' randomization assignments. The families will be instructed not to share this information with the assessors.
 
Different assessors will be responsible for administration of the DAS-II and VABS-II. All assessments will be administered by qualified study personnel. The DAS-II will be administered by a trained practitioner. Shire will have no access to unblinded DAS-II and VABS-II data during the study.
 
The separate substudy is open label and non-randomized, with a single idursulfase-IT treated arm.

----------	--

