[Appendix 5](#) of the protocol Amendment 5 for details. Given that uncertainty around this variability estimate remained, a second BVA using the same approach as specified in [Appendix 5](#) of the protocol Amendment 5 was performed to confirm the estimate after approximately 27 patients completed the Week 52 primary endpoint assessment. Based on this second blinded assessment, the sample size was set to 48 patients while maintaining the 2:1 allocation ratio. As there was no treatment comparison involved, no inflation of the type I error from this procedure was expected, and no adjustment to the significance levels for the final analysis was necessary.

Patients will be randomized (open-label, assessor-blinded) in a 2:1 allocation ratio between the idursulfase-IT treatment regimen and no IT treatment groups. Although this is a multi-center study, the randomization will not be stratified by center. The baseline GCA score (at Screening Visit) is expected to be a key prognostic factor. Therefore, the randomization will be stratified according to baseline GCA score: ≤ 70 versus > 70 . The randomization schedule will be generated and administered centrally by Pharmaceutical Product Development, LLC (PPD), independent of the sponsor's project team. There is no replacement of patients who do not complete the study.

In a separate substudy, additional patients with cognitive impairment may be enrolled who are below the age of 3 years at the time of informed consent. All patients meeting eligibility criteria for the substudy will be enrolled until enrollment for the pivotal study is completed. There is no target sample size. Such patients are ineligible for the pivotal trial and will not be randomized, but will receive idursulfase-IT treatment monthly.

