8. STATISTICAL/ANALYTIC ISSUES

8.1 Adjustment for Covariates

Analyses of the change from baseline in efficacy endpoints utilizing MMRM methodology will adjust for the baseline score of the parameter of interest as a continuous covariate in the model. As the randomization of the study is stratified by the baseline GCA classification factor (either ≤ 70 or > 70), MMRM analyses will also take into account the GCA strata as a classification factor. The baseline age group (either < 6 years or ≥ 6 years) is also a categorical covariate in the MMRM analysis.

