9.2.5 Sample SAS code for rate of change in GCA score analysis

```
ods output ANOVA=ANOVA ParameterEstimates=Parms;  
proc reg data = subject_data ;  
  model GCA = VisitWk ;  
run ;Linear regression fit for individual subject data to calculate individual slope.
```

```
data weight;  
  set ANOVA(drop=Model DEPENDENT DF SS FVALUE PROBF);  
  weight=1/(1+MS);  
  if SOURCE='Error';  
run;
```

Two sample comparison:

```
proc glm;  
  class Trt;  
  model weighted_slope =trt;  
  lsmeans trt / pdiff CL;  
run;
```

where weighted slope=1/(1+MSE from linear regression fit)*slope.

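### The exploratory GCA slope comparison leaves out the baseline GCA stratum used for randomization; if that stratum predicts slope, the test is conservative and its interval somewhat too wide

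*SAP*

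**What the plan says.** The SAP lists one exploratory efficacy endpoint for the pivotal study: each patient's slope from a linear regression of GCA on time.

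- **Method (SAP 6.7.5.4).** "The slope estimate will be compared between the two treatment groups in HIT-HGT-094 using one-way ANOVA". Eligibility: "Only subjects with at least 3 available GCA scores will be included in this analysis". Response: "The response variable in the ANOVA model is the weighted linear regression slope", with weight 1/(1+MSE).
- **Code (SAP 9.2.5).** The only classification variable is `Trt`, and the model statement is "model weighted_slope =trt".
- **Protocol 10.5.4.** The slopes "will be compared between treatment groups using the two-sample t-test", again without adjustment, so the omission did not begin with the SAP.
- **Randomization.** "The randomization is stratified by baseline GCA score" (SAP 4.1), cut at 70. The reason is in SAP 4.2: "The baseline GCA score (at Screening Visit) is expected to be a key prognostic factor".
- **Other analyses.** SAP 8.1 says that "MMRM analyses will also take into account the GCA strata as a classification factor", because randomization was stratified by it. That sentence covers MMRM analyses only. ANCOVA-WOCF and the pattern-mixture analysis (SAP 8.7) have the stratum as a model term. The van Elteren tests (SAP 6.7.5.1, 6.7.5.3 and 8.7) stratify by it. Nothing brings it into the slope model.

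**The concern.** When patients are allocated 2:1 within each GCA stratum, the strata are balanced across arms and a difference in mean slope between strata largely cancels from the treatment contrast. A treatment-only model does not use this. It leaves the between-stratum variance in the residual, so the standard error is larger than the true sampling variability of the contrast. The interval is then too wide and the test rejects less often than its nominal level.

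The same SAP revision that added the slope analysis also replaced the unstratified Wilcoxon test by van Elteren, on the ground that stratifying does better when stratum effects are large. The slope test was left unstratified and no reason is given. What is at stake is precision in a supportive result.

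**Working it through.** **Figures in the plan.** The documents give no power or error rate for the slope test. The nearest stated figure is 80% power for the primary endpoint (48 patients, 2:1, difference 11, SD 11.6, 10% missing). A two-sample t-test gives 81.8% with 28.8 and 14.4 evaluable patients, and 80.7% with 28 and 14. The figure reproduces, so SD 11.6 is used below.

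**Slope SD.** Visits are at weeks 0, 16, 28, 40 and 52 (mean 27.2), so Sxx = 27.2² + 11.2² + 0.8² + 12.8² + 24.8² = 1644.8. The covariance is that of SAP Appendix III (SDs 3, 5, 8, 10; AR(1), ρ = 0.8), scaled by 11.6/10 = 1.16. The slope SD is 0.226 points/week, about 11.7 points/year.

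**Approximate loss on the plain slope.** For two equal strata whose mean slopes differ by Δ in both arms:

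- variance added to the residual = Δ²/4
- interval width ratio ≈ √(1 + (Δ²/4)/11.7²)
- type I error ≈ P(|t₄₆| > 2.013 × ratio)

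| Δ (points/year, assumed) | Δ²/4 | R² | Width ratio | Type I error |
|---|---|---|---|---|
| 5 | 6.25 | 4% | 1.02 | 4.5% |
| 8 | 16 | 10% | 1.06 | 3.9% |
| 10 | 25 | 15% | 1.09 | 3.4% |

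**Simulation on the plain slope** (20,000 trials per case, 16:8 allocation within each of two strata of 24):

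| Δ | Type I error, treatment only | Type I error, with stratum | Mean 95% interval width, treatment only vs with stratum |
|---|---|---|---|
| 5 | 4.3% | 4.8% | 14.7 vs 14.4 |
| 8 | 3.9% | 5.0% | 15.3 vs 14.4 |
| 10 | 3.4% | 5.1% | 15.7 vs 14.4 |

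A separate simulation with permuted blocks of 3 (block size assumed), indexed by R², agrees. At R² = 0 the two models both reject 4.9% of the time, with equal widths. At R² = 0.10 they reject 3.8% and 4.9%, with the treatment-only interval 6% wider. Results are nearly the same with 42 patients or with strata of 33 and 15.

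**Simulation on the SAP's response, slope × 1/(1+MSE)** (same setup, mean decline of 12 points/year assumed). The intervals are 0.9%, 2.3% and 3.6% wider for Δ = 5, 8 and 10. Type I error is 4.1%, 3.9% and 3.7% without the stratum, and 4.4–4.5% with it. The multiplier adds noise unrelated to the stratum, so the stratum explains less of this response. Adding the stratum does not bring the test back to 5%.

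**Stratum difference in controls only.** On the plain slope the treatment-only interval is 0.2–0.9% wider. Power for an assumed treatment difference of 9 points/year, without vs with the stratum, is 67.9 vs 68.1% (Δ = 5), 67.3 vs 67.6% (Δ = 8) and 67.4 vs 68.0% (Δ = 10). On the SAP's response the power gap is at most 0.5 percentage points.

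**The case against.** The case for leaving the analysis alone is substantial.

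- **The loss is conditional.** A reader might infer that the interval is too wide as a matter of fact, or that the plan expects decline to differ between strata. SAP 4.2 supports neither. It calls baseline GCA prognostic, gives no effect size and does not mention slope. The differences of 5, 8 and 10 points/year are assumptions, and 10 is large beside the annual fall of 11 to 14 points that Protocol 4.2 expects without effective treatment. This stands.
- **A material power loss is not shown.** If the stratum difference is the same in both arms, power on the plain slope for 9 points/year is 67%, 65% and 62%, against about 69% with the stratum. But the design alternative has treatment stabilising decline, with treated patients losing about 2 points in all. A stratum difference would then sit mainly in the controls, where omitting the stratum costs almost nothing. This stands too.
- **The analysis is exploratory.** It lies outside Families 1 to 3, its p-value is read descriptively, and the error is conservative. A reader who infers a threat to the primary result or a false-positive risk would be wrong.
- **Appendix III found nearly identical results with the stratum added.** This does not answer the point. Its simulation assigns treatment by a Bernoulli draw and uses mean changes that do not depend on baseline GCA, so it could not have shown the loss.

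The objections limit the size and severity. None gives a reason to omit the stratum: with no stratum effect, including it costs nothing measurable.

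**Conclusion.** The point holds as a low-severity, conditional one. The slope model omits the randomization stratum that the trial's other main comparisons include. If the stratum predicts slope equally in both arms, the test is conservative. For assumed differences of 5 to 10 points/year, the interval is about 2% to 9% wider on the plain slope and about 1% to 4% wider on the response the SAP defines. If the difference is confined to controls the loss is under 1%, and with no stratum effect it is nil. These figures rest on the Appendix III covariance scaled to SD 11.6, 48 patients with complete data, and stratum effects that the documents do not give. The documents do not support calling the analysis invalid or anti-conservative, and the primary, key secondary and gated conclusions are unaffected.

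**What to change.** In SAP 6.7.5.4, replace the one-way ANOVA by a linear model with treatment and the GCA randomization stratum (≤70, >70). In SAP 9.2.5 use:

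`class Trt GCAclass; model <response> = Trt GCAclass; lsmeans Trt / pdiff cl;`

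Here `<response>` is whichever slope response the SAP defines. Whether that should be the slope multiplied by 1/(1+MSE) or the plain slope is a separate question that this change does not settle, and the response should not be altered as a side effect of adding the stratum.

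The cost is one sentence, one model term and one degree of freedom, with no new data. It is best done before database lock.
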